5.1.2 Part B (Single Dose SC Administration)

Part B is designed to assess safety, tolerability, and PK of LY3451838 after SC administration of LY3451838. A single dose of LY3451838 or placebo will be administered SC in up to 2 cohorts (Cohorts 7 and 8) of 8 subjects each, in a 6:2 ratio. Cohort 7 dosing may be initiated after safety and tolerability data have been reviewed from the first 3 cohorts in Part A as described in Section 7.4.1, and may be conducted in parallel with Cohort 4 dosing in Part A. The planned dose level is 250 mg; however, the dose level may be adjusted based on all available data from the first 3 cohorts of Part A, and will be matched to that used in Cohort 3. Safety, tolerability, and PK data from Cohort 7 will be reviewed to determine if Cohort 8 is necessary to explore additional properties of SC dosing regimen, such as different LY3451838 concentration in the formulation, however, the dose for Cohort 8 will match the dose tested in Cohort 7.

Sentinel dosing will not be implemented for Part B because the dose and exposure is expected to not exceed that of Cohort 3 in Part A.

Eligible subjects will be admitted to the CRU on Day -1. LY3451838 or placebo will be administered SC on Day 1, with maximal number of injections not exceeding 4. Subjects will be discharged after completion of all Day 3 activities; and will return to the CRU for safety, PK, and immunogenicity follow-up and end-of-study visits per Section 2.

Study governance is described in detail in [Appendix 3](#).

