5.4 Scientific Rationale for Study Design

This study is designed to evaluate safety, tolerability, and PK of LY3451838 after single IV and SC dose administration in healthy subjects to provide the most unbiased assessment of safety and tolerability in this first-in-human study.

Hypersensitivity reactions, including both acute hypersensitivity reactions and immune complex diseases, are potential risks for all therapeutic antibodies, including LY3451838. Subjects with a history of clinically significant hypersensitivity reactions / conditions, or autoimmune diseases are excluded from the study to minimize risks for hypersensitivity reactions in the subjects in this study, and to avoid confounded interpretation of the safety data. Additional measures will be implemented to monitor and manage infusion reactions (Section 7.4.3.2), immunogenicity, and hypersensitivity reactions (Section 9.6.1). While vasculitis observed in the monkey toxicology studies was attributed to immune complex deposition, additional precautions, such as reviewing PK data before each dose escalation, limiting the dose range and implementing the exposure to that of the monkey NOAEL are designed into the protocol to address the uncertainty of the mechanism for vasculitis.

Because of the distribution of PACAP in the nervous system, and to follow-up on the subtle non-adverse changes in the neurological examination in the 2-month monkey toxicology study, neurological examinations will be performed to detect any early signals on the effects of LY3451838 on the nervous system.

Pharmacokinetic data will be used to guide dose escalation for all cohorts in Part A of the study; dose modification criteria are described in Section 7.4.1. Because the exposure after SC dosing is

[figure not shown]
expected to be less than with IV dosing for the same dose, sentinel dosing is not required in Part B of the study.

The predicted half-life of LY3451838 is 12 days, based on the allometric scaling from monkey PK data. A parallel-group design is used in both Part A and Part B of the study to avoid a prolonged washout period between doses and to avoid the potential to confound treatment-emergent antidrug antibody (TEADA) assessment. The monitoring period for this study is approximately 20 weeks after the last dose. This monitoring period duration supports adequate immunogenicity monitoring during the washout of LY3451838.

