8.1 Discontinuation from Study Treatment

Subjects may be discontinued from the study treatment if an SAE occurs during the study drug infusion, or injections irrespective of causality.

Subjects in Part A who discontinue from treatment before infusion end for any reason should complete ED procedures per Section 2 of this protocol, after AE follow up is completed.

Subjects in Part B who discontinue from the treatment before all injections have been completed may be allowed to complete the rest of the study activities (according to the planned Schedule of Activities in Section 2). The decision to allow a subject to complete the study activities should be made jointly by both sponsor and investigator, and only if the reason for discontinuation does not affect the interpretation of the safety and PK/PD data, and continuation of the study activities does not increase risks for the subject. If it is decided that the subject should be discontinued from the study, subject should complete ED procedures according to Schedule of Activities.

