9.2 Adverse Events

A clinical trial AE is any untoward medical event associated with the use of a drug or drug delivery system in humans, whether or not it is considered related to that drug or drug delivery system.

Investigators are responsible for monitoring the safety of subjects who have entered this study and for alerting Lilly or its designee to any event that seems unusual, even if this event may be considered an unanticipated benefit to the subject.

The Investigator is responsible for the appropriate medical care of subject during the study.

Investigators must document their review of each laboratory safety report.

The Investigator remains responsible for following, through an appropriate health care option, AEs that are serious or otherwise medically important, considered related to the study drug or the study related procedure, or that caused the subject to discontinue the study drug before completing the study. The subject should be followed until the event resolves, stabilizes with appropriate diagnostic evaluation, or is reasonably explained. The frequency of follow-up evaluations of the AE is left to the discretion of the Investigator.

After the informed consent form (ICF) is signed, the CRU personnel will record, via EDC, the occurrence and nature of each subject's preexisting conditions, including clinically significant signs and symptoms of the disease under treatment in the study. Additionally, site personnel will record any change in the condition(s) and the occurrence and nature of any AEs.

Planned surgeries should not be reported as AEs unless the underlying medical condition has worsened during the course of the study.

Injection site reactions should be captured as AEs. Additional information including the time of day, time relative to injection, size, amount of erythema, induration, and pruritus will be recorded.

If a subject's study drug is discontinued as a result of an AE, CRU personnel must report this to Lilly or its designee via EDC.

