9.2.1 Serious Adverse Events

An SAE is any AE from this study that results in one of the following:

- death
- initial or prolonged inpatient hospitalization
- a life-threatening experience (that is, immediate risk of dying)
- persistent or significant disability/incapacity
- congenital anomaly/birth defect
- important medical events that may not be immediately life-threatening or result in death or hospitalization but may jeopardize the subject or may require intervention to prevent one of the other outcomes listed in the definition above.

The CRU personnel must alert the Lilly medical monitor, or its designee, of any SAE as soon as practically possible.

Additionally, CRU personnel must alert Lilly Global Patient Safety, or its designee, of any SAE within 24 hours of Investigator awareness of the event via a Sponsor-approved method. If alerts are issued via telephone, they are to be immediately followed with official notification on study-specific SAE forms. This 24-hour notification requirement refers to the initial SAE information and all follow-up SAE information.

Although all AEs are recorded in the case report form or EDC after signing informed consent, SAE reporting to the Sponsor begins after the subject has signed informed consent and has received the study drug. However, if an SAE occurs after signing informed consent, but prior to receiving the study drug, AND is considered Reasonably Possibly Related to a study procedure then it MUST be reported.

Investigators are not obligated to actively seek AEs or SAEs in subjects once they have discontinued from and/or completed the study. Serious adverse events will be collected for

30 days after the last dose of study drug. However, if the Investigator learns of any SAE, including a death, at any time after a subject has been discharged from the study, and he/she considers the event reasonably possibly related to the study treatment or study participation, the Investigator must promptly notify Lilly.

Pregnancy (maternal or paternal exposure to the study drug) does not meet the definition of an adverse event. However, to fulfill regulatory requirements any pregnancy should be reported following the SAE process to collect data on the outcome for both mother and fetus.

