9.6 Pharmacodynamics

9.6.1 Immunogenicity Assessments

At the visits and times specified in the Schedule of Activities (Section 2), venous blood samples of approximately 10 mL each will be collected to determine antibody production against LY3451838. In the event of drug hypersensitivity reactions (immediate or non-immediate), additional samples will be collected as close to the onset of the event as possible, at the resolution of the event, and 30 days following the event. Blood samples for LY3451838 and PACAP concentration will be collected concurrently with these unscheduled immunogenicity

samples. Instructions for the collection and handling of blood samples will be provided by the sponsor. The actual date and time of each sampling will be recorded.

Immunogenicity will be assessed by a validated assay designed to detect ADAs in the presence of the study drug at a laboratory approved by the sponsor. Antibodies may be further characterized and/or evaluated for their ability to neutralize the activity of the study drug.

Samples will be retained for a maximum of 15 years after the last subject visit, or for a shorter period if local regulations and Ethical Review Boards (ERBs) allow, at a facility selected by the sponsor. The duration allows the sponsor to respond to future regulatory requests related to the study drug. Any samples remaining after 15 years will be destroyed.

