	Cohort 1 25mgIV N=XX	Cohort 2 75mgIV N=XX	Cohort 3 250mgIV N=XX	Cohort 4 500mgIV N=XX	Cohort 5 1000mgIV N=XX	Cohort 6 1500mgIV N=XX	Cohort 7 250mgSC N=XX		
Post-baseline Visit #1	N	xx	xx	xx	xx	xx	xx	xx	xx
	YES	x(xx.x%)	x(xx.x%)	x(xx.x%)	x(xx.x%)	x(xx.x%)	x(xx.x%)	x(xx.x%)	x(xx.x%)
	NO	x(xx.x%)	x(xx.x%)	x(xx.x%)	x(xx.x%)	x(xx.x%)	x(xx.x%)	x(xx.x%)	x(xx.x%)
Post-baseline Visit #2	N	xx	xx	xx	xx	xx	xx	xx	xx
	YES	x(xx.x%)	x(xx.x%)	x(xx.x%)	x(xx.x%)	x(xx.x%)	x(xx.x%)	x(xx.x%)	x(xx.x%)
	NO	x(xx.x%)	x(xx.x%)	x(xx.x%)	x(xx.x%)	x(xx.x%)	x(xx.x%)	x(xx.x%)	x(xx.x%)

...

The baseline is the measurement at Visit 3 prior to dosing, or Visit 2 whichever is the last available one.  
 Program: 14.3.4.4.xxx.sas

Eli Lilly and Company - PROTOCOL: J1H-MC-LAJA  
 A Safety, Tolerability, and Pharmacokinetics Study of LY3451838 in Healthy Subjects

Table 14.3.4.5  $\bar{T}$  Immunogenicity (Safety)

	LY3451838							Total LY	Placebo
	Cohort 1 25mgIV N=XX	Cohort 2 75mgIV N=XX	Cohort 3 250mgIV N=XX	Cohort 4 500mgIV N=XX	Cohort 5 1000mgIV N=XX	Cohort 6 1500mgIV N=XX	Cohort 7 250mgSC N=XX		
Subject Evaluable for TEADA*	x (xx.x%)	x (xx.x%)	x (xx.x%)	x (xx.x%)	x (xx.x%)	x (xx.x%)	x (xx.x%)	x (xx.x%)	x (xx.x%)
Subject with ADA Detected at Baseline	x (xx.x%)	x (xx.x%)	x (xx.x%)	x (xx.x%)	x (xx.x%)	x (xx.x%)	x (xx.x%)	x (xx.x%)	x (xx.x%)
Subject with TEADA+ at Post-baseline**	x (xx.x%)	x (xx.x%)	x (xx.x%)	x (xx.x%)	x (xx.x%)	x (xx.x%)	x (xx.x%)	x (xx.x%)	x (xx.x%)
Treatment-Induced	x (xx.x%)	x (xx.x%)	x (xx.x%)	x (xx.x%)	x (xx.x%)	x (xx.x%)	x (xx.x%)	x (xx.x%)	x (xx.x%)
Treatment-Boosted	x (xx.x%)	x (xx.x%)	x (xx.x%)	x (xx.x%)	x (xx.x%)	x (xx.x%)	x (xx.x%)	x (xx.x%)	x (xx.x%)

\* Subjects evaluable for TEADA if there is at least one baseline assessment and at least post-baseline assessment of ADA.

\*\* Treatment-emergent ADAs are defined as those with a titer 2-fold (1dilution) greater than the minimum required dilution if no ADAs were detected at baseline (treatment-included ADA) or those with a 4-fold (2 dilutions) increase in titer compared to baseline if ADAs were detected at baseline (treatment-boosted ADA).

Program: 14.3.4.5.xxx.sas

Eli Lilly and Company - PROTOCOL: J1H-MC-LAJA  
 A Safety, Tolerability, and Pharmacokinetics Study of LY3451838 in Healthy Subjects

Table 14.3.4.6  $\bar{T}$  PACAP Concentration (Safety)

3451838P		LY3451838							Total LY	Placebo

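### Protocol 8.1 can end follow-up of a partly dosed Part B subject because of why dosing stopped, even when staying would be safe

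*Protocol*

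**What the plan says.** Protocol Section 5.1.2 allows the subcutaneous dose to be split, "with maximal number of injections not exceeding 4", so a subject can receive part of a dose.

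Section 8.1 then treats the two parts differently.

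- **Part B.** A subject who stops before the last injection may be permitted to finish the schedule. The sponsor and investigator decide together, and two conditions must both hold. Staying is open "only if the reason for discontinuation does not affect the interpretation of the safety and PK/PD data", and continuing must not add risk. A subject who is discontinued has ED procedures.
- **Part A.** There is no option to stay. Anyone who stops before the infusion ends is to have ED procedures, whatever the reason, once AE follow-up is finished.

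Footnote a of the Schedule of Activities makes the ED visit equal to Visit 16, which includes an ADA sample. After that, Section 9.2.1 says: "Investigators are not obligated to actively seek AEs or SAEs in subjects once they have discontinued from and/or completed the study".

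Section 5.4 explains the 20-week observation period: "This monitoring period duration supports adequate immunogenicity monitoring during the washout of LY3451838".

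**The concern.** Safety is the primary objective, and follow-up should not end for a reason tied to the outcome being measured. The Part B rule permits that. A subject whose injections were stopped because of a reaction may be judged to have a reason that affects interpretation of the safety data, and would then leave the schedule although continuing carries no added risk. A subject whose injections stopped for an administrative reason would more easily stay. The ADA visits fall under the same test, because immunogenicity sits under Section 9.6, Pharmacodynamics.

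The subjects most worth watching for later events or antibodies could therefore be the ones watched for the shortest time.

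**Working it through.** **Step 1. Set the two conditions side by side.** They are joined, so both must hold.

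| Reason affects interpretation? | Continuing adds risk? | May stay under 8.1? |
|---|---|---|
| No | No | Yes, by joint decision |
| No | Yes | No |
| Yes | Yes | No |
| Yes | No | No |

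The last row is the point: the subject could safely stay but may not. The test also looks at the reason for stopping, not at how much drug was given. Two subjects with the same shortfall can be treated differently.

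**Step 2. Does the condition protect an analysis?** Protocol 10.3 analyses safety for all enrolled subjects, complete or not. SAP 5.1 includes anyone enrolled who received any study drug. Protocol 10.3.2.1 includes every subject dosed with LY3451838 who has evaluable concentrations. A partly dosed subject is in the safety analysis either way, and an active one is in the PK analysis if concentrations are evaluable. The condition only cuts short what is observed.

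**Step 3. ADA samples.** Appendix 5 plans 7 per subject. The schedule row has predose plus Days 5, 9, 22, 43, 71 and 141: 1 + 6 = 7, which agrees. The SAP copy of the schedule has the same days. For a hypersensitivity reaction on Day 1, the last extra ADA sample falls 30 days later, at about Day 31. Scheduled samples after that are Days 43, 71 and 141, or 3 of 6. The marked-up schedule in Appendix 7 is extracted with other days (7, 15, 29, 57, 85, 141), but the count after Day 31 is again 3 of 6.

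**Step 4. Active AE search lost by one subject.** Full follow-up is 141 − 1 = 140 days. The documents give no exit day, so three are assumed; Day 3 is the extreme.

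| Assumed exit | Days lost | Share of 140 | Scheduled post-dose ADA days not reached |
|---|---|---|---|
| Day 31 | 141 − 31 = 110 | 78.6% | 3 of 6 |
| Day 15 | 141 − 15 = 126 | 90.0% | 4 of 6 |
| Day 3 | 141 − 3 = 138 | 98.6% | 6 of 6 |

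In each case one ADA sample is taken at the ED visit, and extra ones follow if there was a hypersensitivity reaction. The day counts give no credit for 30-day collection of serious AEs, which runs to about Day 31. For serious AEs alone, the loss is about 110 days in every row.

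**Step 5. Effect on Cohort 7**, with 6 planned active subjects and one leaver. Full follow-up is 6 × 140 = 840 subject-days.

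- Exit Day 31: (5 × 140 + 30)/840 = 86.9% kept.
- Exit Day 3: (5 × 140 + 2)/840 = 83.6% kept.
- If the leaver is replaced, seven subjects make 980 days: (840 + 30)/980 = 88.8% and (840 + 2)/980 = 85.9%.

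Replacement restores the number of completers but not the leaver's own later data.

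**The case against.** The strongest reply is that little is really lost.

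- The ED visit repeats everything planned for Visit 16.
- The introduction to Section 8 requires Section 9.2 follow-up after every premature discontinuation. Section 9.2 keeps the investigator responsible for an AE that "caused the subject to discontinue the study drug before completing the study".
- Serious AEs are collected for 30 days, and possibly related ones that the investigator learns of later must still be reported.
- After a hypersensitivity reaction, Section 9.6.1 adds ADA samples at onset, "at the resolution of the event, and 30 days following the event". Section 9.4.5.2 adds stored serum 4 to 6 weeks after a moderate or severe reaction, so about Day 29 to Day 43 for a Day 1 event.
- Section 9.6.1 specifies "a validated assay designed to detect ADAs in the presence of the study drug", so early samples are not worthless while drug is circulating.

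All of this stands and limits the size of the point. It does not answer it: none of these provisions restores active search for new AEs or the later scheduled ADA visits.

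It is also fair to say that Part B is the more lenient part. Part A offers no stay at all and holds 36 of the 42 planned active subjects in Cohorts 1 to 7 (6 × 6 = 36, plus 6 in Cohort 7). That is a reason to look at Part A as well, not to leave Part B as it is.

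A reader might infer that 8.1 requires removal of anyone whose injections were stopped for a reaction. The text does not say so. It names no event and leaves the matter to joint judgement, so removal is possible, not automatic.

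A reader might also infer that early leavers distort the treatment-emergent ADA (TEADA) table, because the SAP shell says "Subjects evaluable for TEADA if there is at least one baseline assessment and at least post-baseline assessment of ADA" and sets no minimum follow-up. The documents do not support a change there. TEADA is an exploratory, descriptive endpoint, early leavers are reported under a stated rule, and results by subject are available in Listing 9 or the raw listings that may replace it.

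**Conclusion.** The point holds and is minor. Section 8.1 can end a Part B subject's follow-up for a reason linked to the safety outcome when staying would be safe, and no analysis needs that condition. The event that stopped dosing is still followed and reported, so the exposure is limited to later AEs and later ADA results in such a subject.

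The size rests on three assumptions that the documents do not settle: partial dosing is rare, one active subject is affected, and exit falls between Day 3 and Day 31. On these, that subject loses 79% to 99% of the active search period, and Cohort 7 keeps about 84% to 87% of its planned active subject-days without replacement. No primary analysis changes.

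**What to change.** In Section 8.1, Part B, delete the interpretation condition for safety and immunogenicity follow-up. Suggested wording: a subject who receives part of the dose continues the scheduled safety and ADA visits unless continuing increases risk, consent is withdrawn, or another ground in Section 8.2 applies. Investigator decision stays among those grounds, so this changes the default and does not guarantee follow-up.

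Consider the same default for Part A. Section 7.4.3.2 could be aligned with it: after an infusion reaction it refers to follow-up under Section 2 without saying whether that means the ED visit or the full schedule.

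The cost is one clause and a few already scheduled visits for a rare subject. SAP Section 6 reports nobody in Cohort 8 at data lock, so the edit may help only later protocols.

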8.1.1 Discontinuation of Inadvertently Enrolled Subjects

If the Sponsor or investigator identifies a subject who did not meet enrollment criteria and was inadvertently enrolled, a discussion must occur between the Lilly medical monitor and the investigator to determine if the subject may continue in the study. If both agree it is medically appropriate to continue, the investigator must obtain documented approval from the Lilly medical monitor to allow the inadvertently enrolled subject to continue in the study with or without continued treatment with study drug.

8.2 Discontinuation from the Study

Subjects will be discontinued in the following circumstances:

- Enrollment in any other clinical study involving any study drug or enrollment in any other type of medical research judged not to be scientifically or medically compatible with this study
- Participation in the study needs to be stopped for medical, safety, regulatory, or other reasons consistent with applicable laws, regulations, and good clinical practice (GCP)
- Investigator Decision
 - the investigator decides that the subject should be discontinued from the study
 - if the subject, for any reason, requires treatment with another therapeutic agent that has been demonstrated to be effective for treatment of the study indication, discontinuation from the study occurs prior to introduction of the new agent
- Subject Decision

- The subject requests to be withdrawn from the study.
- Termination of the study by the Sponsor or regulatory authorities

8.3 Subjects Lost to Follow-up

A subject will be considered lost to follow-up if he or she repeatedly fails to return for scheduled visits and is unable to be contacted by the CRU. The CRU personnel are expected to make diligent attempts to contact subjects who fail to return for a scheduled visit or were otherwise unable to be followed up by the CRU.

Subjects who withdraw from the study before completion of all study activities may be replaced at the discretion of the Sponsor.

9 Study Assessments and Procedures

Section 2 lists the Schedule of Activities, detailing the study procedures and their timing (including tolerance limits for timing).

Appendix 2 lists the laboratory tests that will be performed for this study.

Appendix 5 provides a summary of the maximum number and volume of invasive samples, for all sampling, during the study.

The specifications in this protocol for the timings of safety and sample collections are given as targets to be achieved within reasonable limits. Modifications may be made to the time points based upon emerging clinical information. The scheduled time points may be subject to minor alterations; however, the actual time must be recorded correctly in the EDC. Failure or delays (i.e. outside stipulated time allowances) in performing procedures or obtaining samples due to legitimate clinical issues (e.g. equipment technical problems, venous access difficulty, or subject defaulting or turning up late on an agreed scheduled procedure) will not be considered as protocol deviations but the CRU will still be required to notify the sponsor in writing via a file note for data reconciliation purpose.

Unless otherwise stated in subsections below, all samples collected for specified laboratory tests will be destroyed within 60 days of receipt of confirmed test results. Certain samples may be retained for a longer period, if necessary, to comply with applicable laws, regulations, or laboratory certification standards.

